## **8. STATISTICAL AND QUANTITATIVE ANALYSES**

### **8.1 Statistical Methods**

In general, summary tabulations will be presented by treatment arm and will display the number of observations, mean, standard deviation, median, minimum, and maximum for continuous variables, and the number and percent per category for categorical data. The Kaplan-Meier survival curves and 25th, 50th (median), and 75th percentiles will be provided along with their 2-sided 95% CIs for time-to-event data.

## **Brentuximab vedotin (ADCETRIS®)**

### **Clinical Study Protocol C25003 Amendment 7, EudraCT: 2011-005450-60**

The statistical methods are outlined below; analysis details will be provided in the statistical analysis plan (SAP). The SAP will be written by Millennium and will be finalized prior to the formal interim analysis.

Deviations from the statistical analyses outlined in this protocol will be indicated in the SAP; any further modifications will be noted in the final clinical study report.

#### **8.1.1 Determination of Sample Size**

The primary endpoint of the study is mPFS, and the study is powered on the following assumption: a 2-year mPFS of 81% for patients in the A+AVD treatment group versus 73% for patients in the ABVD treatment group (HR=0.67; assuming a decrease in the PFS event rate after 2 years). A total of 260 mPFS events will provide 90% power to detect a hazard ratio of 0.67 at a 1-sided significance level of 0.025 using a log-rank test. Approximately 1240 patients will be randomized to achieve (with 95% probability) 260 mPFS events in approximately 60 months, assuming 36 months of accrual, a 5% annual dropout rate, and 24 months of mPFS follow-up after last patient in.

#### **8.1.2 Randomization and Stratification**

The randomization scheme will be generated by Millennium. Prior to dosing, a randomization number will be assigned to each patient. The randomization schedule also includes the study specific identifiers (company name, protocol name, and protocol number) and the date and time the schedule was generated.

Patients will be randomized in an overall ratio 1:1 to A+AVD or ABVD. Patients will be stratified by region (Americas vs Europe vs Asia) and number of IPFP risk factors (0-1 vs 2-3 vs 4-7).

#### **8.1.3 Populations for Analysis**

The populations used for analysis will include the following:

- Safety population: patients who receive at least 1 dose of study drug will be used for all safety analyses. All patients in the safety population will be analyzed according to the actual treatment received.
- Intent-to-Treat (ITT) population: all patients randomized to treatment. All patients in the ITT population will be analyzed according to the treatment they were randomized to receive and not according to what they actually received, if different.

- Per-Protocol (PP) population: a subset of ITT patients who do not have a major protocol violation as determined by the project clinician. All decisions to exclude patients from the PP population will be made prior to database lock.
- Response-Evaluable population: all patients with diagnosis as confirmed by an independent pathology review facility, with measurable disease at baseline, who receive at least 1 dose of study drug, and have at least 1 postbaseline response assessment.
- PK population: patients with sufficient dosing and PK data to reliably estimate PK parameters as determined by a clinical pharmacologist. The PK population will be used for PK analyses.
- Pharmacodynamics population: patients with sufficient dosing and sufficient pharmacodynamics data to reliably measure pharmacodynamics parameters will be used for pharmacodynamics analyses.

#### **8.1.4 Procedures for Handling Missing, Unused, and Spurious Data**

All available efficacy and safety data will be included in data listings and tabulations. The relevance of missing sample data will be assessed. Details on any sensitivity analyses and data handling details regarding issues such as missing data will be discussed in the SAP.

Data that are potentially spurious or erroneous will be examined according to standard data management operating procedures.

#### **8.1.5 Demographic and Baseline Characteristics**

Demographic and baseline characteristics will be summarized, including gender, age, race, weight, height, BSA, primary diagnosis, and other parameters as appropriate. No inferential statistics will be carried out.

#### **8.1.6 Efficacy Analysis**

All efficacy evaluations will be conducted using the ITT population unless otherwise specified.

##### **8.1.6.1 Analysis of Primary Efficacy Endpoint**

Modified PFS per IRF will be used for the primary efficacy analysis.

**Modified Progression-Free Survival**

As PET-negative CR is the expected therapeutic outcome in frontline HL, the definition of PFS has been modified to reflect current standards of care. Modified PFS per IRF will be analyzed based on the ITT population using a stratified log-rank test. Modified PFS is defined as the time from the date of randomization to the date of the first of (1) documentation of PD; (2) death due to any cause; (3) for patients who are confirmed noncomplete responders per IRF, receipt of anticancer chemotherapy or radiotherapy for HL after completion of frontline therapy, as defined in [Table 8-1](#); these patients' mPFS event date will be the date of the first PET scan post completion of frontline therapy demonstrating the absence of a CR, defined as a Deauville score of  $\geq 3$ .

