**Brentuximab vedotin (ADCETRIS®)****Clinical Study Protocol C25003 Amendment 7, EudraCT: 2011-005450-60**

performed every 3 months during the first year of posttreatment disease follow-up, then every 6 months until study closure (5 years after the last patient is enrolled). If, for any reason other than death or documented disease progression, a patient discontinues randomization therapy (A+AVD or ABVD) after Cycle 2 Day 25 but before completion of randomization therapy, every effort must be made to obtain PET and CT scans prior to initiation of subsequent therapy for HL. Responses and relapses will be assessed by an IRF. Evaluations will be performed until progressive disease (PD) is documented, receipt of second-line anticancer therapy for HL (including chemotherapy or radiation), death occurs, or the end of study. Patients will be followed for survival until death or for a minimum of 5 years after enrollment of the last patient.

Deauville scoring (see Section 15.6) per IRF will be used to evaluate the results of patients' Cycle 2 Day 25 PET/CT. Patients whose disease earns a Deauville score of 4 or less will continue study drug treatment according to their randomized arm (ABVD or A+AVD). Patients whose PET-positive disease earns a score of 5 may, at the investigator's discretion, receive an alternative regimen (physician's choice) for the remainder of planned frontline therapy. Patients with a Deauville score of 5 who, at investigator's discretion, are taken off study drug will be continue to be followed for response assessment; switching therapy prior to completion of frontline therapy will not be considered an mPFS progression event. Of further note, any switch in therapy prior to completion of frontline therapy will not be considered an mPFS event.

An interim futility analysis will be conducted when the first approximately 348 patients have completed the regimen to which they were randomized (ie, received the planned study drug regimen with no more than 2 missed doses of A+AVD or ABVD) or have discontinued treatment prior to completion. The final analysis of the mPFS primary endpoint will be conducted when 260 mPFS events occur; an interim analysis of OS will also be conducted at that time. The final analysis of OS will be conducted when 112 deaths occur, approximately 4 years after randomization of the last patient.

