**Brentuximab vedotin (ADCETRIS®)**

**Clinical Study Protocol C25003 Amendment 7, EudraCT: 2011-005450-60**

4. Known cerebral or meningeal disease (HL or any other etiology), including signs or symptoms of PML
5. Symptomatic neurologic disease compromising normal activities of daily living or requiring medications
6. Any sensory or motor peripheral neuropathy
7. Any active systemic viral, bacterial, or fungal infection requiring systemic antibiotics within 2 weeks prior to first study drug dose
8. Prior immunosuppressive chemotherapy, therapeutic radiation, or any immunotherapy (eg, immunoglobulin replacement, other monoclonal antibody therapies) within 12 weeks of first study drug dose
9. Known hypersensitivity to recombinant proteins, murine proteins, or to any excipient contained in the drug formulation of brentuximab vedotin or any component of ABVD
10. Known human immunodeficiency virus (HIV) positive
11. Known hepatitis B surface antigen-positive, or known or suspected active hepatitis C infection
12. Diagnosed or treated for another malignancy within 3 years before the first dose or previously diagnosed with another malignancy and have any evidence of residual disease. Patients with nonmelanoma skin cancer or carcinoma in situ of any type are not excluded if they have undergone complete resection.
13. Any of the following cardiovascular conditions or values within 6 months before the first dose of study drug:
  - A left-ventricular ejection fraction <50%
  - Myocardial infarction within 2 years of randomization
  - New York Heart Association (NYHA) Class III or IV heart failure (see Section 15.4).

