## **Brentuximab vedotin (ADCETRIS®)**

### **Clinical Study Protocol C25003 Amendment 7, EudraCT: 2011-005450-60**

every 6 months until the first of disease progression or study closure. CT scans are required every 12 weeks ( $\pm 1$  week) until 12 months of PTFU and then every 6 months ( $\pm 2$  weeks) until study closure. For patients who have PD, survival/disease status and information regarding the initiation of an alternative lymphoma treatment may be obtained by phone call. To support fertility assessment, any pregnancy occurring in patients or their partners from the date of first dose until the date of study closure should be reported.

Patients who stop treatment for any reason other than PD will continue to have mPFS follow-up visits until the occurrence of PD; the patient withdraws consent for further follow-up; or, the start of another anticancer therapy for patients not in CR after completion of frontline therapy.

Patients will be followed for survival until 5 years from the date of the last patient randomized, or death, whichever occurs first. Survivor information may be collected by methods that include, but are not limited to, telephone, e-mail, mail, or retrieved from online or other databases (eg, social security indexes). In addition, the start of another anticancer therapy will be collected.

See the [Schedule of Events](#) for appropriate assessments during follow-up.

NOTE: Related SAEs must be reported to the Millennium Department of Pharmacovigilance & Risk Management or designee. This includes deaths that the investigator considers related to study drug that occur during the posttreatment follow-up. Refer to Section 10 for details regarding definitions, documentation, and reporting of SAEs.

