**Table 8-1 Completion of Frontline Therapy**

Treatment History	Completion of Frontline Therapy
Did not switch therapy	Upon receipt of planned study drug regimen with no more than 2 missed doses of A+AVD or ABVD a
Switched therapy before completion of A+AVD or ABVD	Upon conclusion of 1 alternative anticancer regimen b for HL subsequent to A+AVD or ABVD discontinuation

a A "missed dose" refers to administration of the full study regimen of either A+AVD or ABVD. Patients may miss individual agents within the A+AVD or ABVD regimen (such as patients who discontinue bleomycin for pulmonary toxicity) without this counting as a missed dose.

b Receipt of chemotherapy OR radiation.

Patients without a documented mPFS event at the time of analysis (defined as PD/relapse, subsequent anticancer therapy for residual disease after completion of planned frontline therapy for HL, or death) will be censored at the date of last response assessment. Detailed handling rules for missing assessments and censoring for the analysis of mPFS will be described in Section 5.8.1.2 of the SAP.

Modified PFS will be tested at a 1-sided 0.025 level at the final analysis.

In addition, a stratified Cox regression model will be used to estimate the hazard ratio and the 95% CI for the treatment effect. The Kaplan-Meier survival curves, 25th, 50th (median), and 75th percentiles (if estimable), along with their 2-sided 95% CIs, will also be presented for each treatment arm.

Sensitivity analyses for mPFS per IRF will be performed using the PP population. Modified PFS per IRF using different censoring approaches will be also analyzed in the ITT population. Details of different censoring approaches and further sensitivity analyses of

mPFS will be included in the SAP. Modified PFS per investigator will also be analyzed similarly using the ITT population.

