5.8.1.1 Definition

mPFS is defined as:

The time from the date of randomization to the date of the first of (1) documentation of progressive disease (PD); (2) death due to any cause; (3) for patients who are confirmed non-complete responders per IRF, receipt of anticancer chemotherapy or radiotherapy for HL after completion of frontline therapy, as defined in [Table 5-1](#); these patients' mPFS event date will be the date of the first PET scan post completion of frontline therapy demonstrating the absence of a CR, defined as a Deauville score of ≥ 3 .

Table 5-1 Completion of Frontline Therapy

Treatment History	Completion of Frontline Therapy
Did not switch therapy	Upon receipt of planned study drug regimen with no more than 2 missed doses of A+AVD or ABVD ^a
Switched therapy before completion of A+AVD or ABVD	Upon conclusion of 1 alternative anticancer regimen ^b for HL subsequent to A+AVD or ABVD discontinuation

a A "missed dose" refers to administration of the full study regimen of either A+AVD or ABVD. Patients may miss individual agents within the A+AVD or ABVD regimen (such as patients who discontinue bleomycin for pulmonary toxicity) without this counting as a missed dose.

b Receipt of chemotherapy OR radiation.

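### The protocol defines the third mPFS event in two ways, so an IRF-confirmed non-complete responder rescued without chemotherapy or radiotherapy may be an event or may be censored near treatment failure.

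*Protocol*

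**What the plan says.** Two wordings of the same event stand in the plan.

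- **Narrow.** Protocol 8.1.6.1 lists as the third mPFS event, "for patients who are confirmed noncomplete responders per IRF, receipt of anticancer chemotherapy or radiotherapy for HL after completion of frontline therapy". SAP 5.8.1.1 has the same limit: "for patients who are confirmed non-complete responders per IRF, receipt of anticancer chemotherapy or radiotherapy for HL after completion of frontline therapy". The Protocol Summary and Protocol 4.1 also name chemotherapy or radiotherapy. The event is dated to the first PET after frontline therapy that shows no CR (Deauville score 3 or more).
- **Broad.** The censoring paragraph under Protocol Table 8-1 restates the mPFS event and there includes "subsequent anticancer therapy for residual disease after completion of planned frontline therapy for HL, or death". No therapy class is named.

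Follow-up also runs on the broad wording. Protocol 7.10 ends mPFS visits at "the start of another anticancer therapy for patients not in CR after completion of frontline therapy". Protocol 4.1 ends disease evaluations at "receipt of second-line anticancer therapy for HL (including chemotherapy or radiation"), where the two classes are given as inclusions and not as a limit.

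SAP Table 5-2 censors a patient without a documented mPFS event at the last adequate assessment. It does the same when an event follows more than one missed visit.

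Neither document says how antibodies, antibody-drug conjugates or other immunotherapies are classed for this component.

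**The concern.** The trigger that ends mPFS visits is wider than the trigger that counts the event. A patient can therefore leave scheduled assessment because of a new treatment for residual disease without that treatment being an event. If nothing else happens that counts, the patient is censored at the last adequate scan, close to the time when frontline therapy was shown to have failed. Such censoring is informative: the censored patient's prognosis is clearly worse than that of the patients who remain at risk.

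Two programmers who each follow the protocol could also derive different primary endpoints from the same data. If the choice is made after treatment-arm results are known, it will look data-driven whichever way it goes.

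**Working it through.** **1. The same patient under each text.** Take a patient with IRF-confirmed non-CR after frontline therapy whose only further treatment is an antibody or immunotherapy, with no documented progression or death.

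| Text | Outcome |
|---|---|
| Protocol 8.1.6.1 numbered definition; SAP 5.8.1.1 | No third-component event |
| Protocol 8.1.6.1 censoring paragraph | Event |
| Protocol 7.10 and 4.1 | Scheduled mPFS visits or evaluations may end |
| SAP Table 5-2, row for no documented event | Censored at last adequate assessment |

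**2. Do the sensitivity analyses cover this patient?** No. The two rows of SAP Table 5-3 on new therapy name only chemotherapy or radiotherapy, and apply only to patients without confirmed non-CR. The third sensitivity analysis in SAP 5.8.2.1 re-dates events that confirmed non-CR already constitutes; it does not say which therapies qualify.

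**3. The plan's own figure.** Protocol 8.1.1 gives 260 events, HR 0.67, one-sided 0.025 and 90% power. By Schoenfeld's formula, events = 4 × (1.960 + 1.282)² / (ln 0.67)² ≈ 262.1, rounded up to 263. Power at 260 events = Φ(√(260/4) × |ln 0.67| − 1.96) = 0.898. The figure reproduces and does not depend on the wording.

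**4. Size under assumptions.** The documents give neither the share of events from the third component nor the mix of rescue treatments, so the following inputs are assumed.

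- Event split: 260 shared in proportion to the 2-year event rates of 27% and 19%, which gives 260 × 0.27/0.46 = 152.6 for ABVD and 107.4 for A+AVD.
- *c*: third component's share of events. *b*, *a*: share of those rescues that are neither chemotherapy nor radiotherapy, in ABVD and A+AVD respectively.
- Every such rescue is treated as a permanently lost event, which is a worst case (see the objection).
- HR′ = 0.67 × (1 − *ca*) / (1 − *cb*). Power = Φ(√65 × |ln HR′| − 1.96), with 260 counted events still reached.

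| *c* | *b* (ABVD) | *a* (A+AVD) | Events lost, ABVD / A+AVD | HR′ | Power |
|---|---|---|---|---|---|
| 20% | equal to *a* | equal to *b* | in proportion | 0.670 | 90% |
| 10% | 10% | 5% | 1.5 / 0.5 | 0.67 × 0.995/0.990 = 0.673 | 89% |
| 20% | 25% | 5% | 7.6 / 1.1 | 0.67 × 0.990/0.950 = 0.698 | about 82% |
| 30% | 50% | 5% | 22.9 / 1.6 | 0.67 × 0.985/0.850 = 0.776 | 53% |
| 20% | 5% | 25% | 1.5 / 5.4 | 0.67 × 0.950/0.990 = 0.643 | 95% |

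The last row reverses the third. Reversing the fourth row as well would give 0.67 × 0.850/0.985 = 0.578, so the worked cases are not a symmetric bound.

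**5. Cross-check by a second approximation.** Use HR = ln(1 − d₁/620) / ln(1 − d₀/620), where d₁ and d₀ are the A+AVD and ABVD events. With d₁ = 107.4 and d₀ = 152.6 the baseline is 0.673. Losing 5 ABVD events alone gives 0.70, and losing 10 gives 0.73. Losing 5 A+AVD events alone gives 0.64. Losing 4 A+AVD and 6 ABVD events gives 0.68. The two methods agree: an unbalanced loss moves the HR, and a balanced loss mainly delays an event-driven analysis.

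**The case against.** The strongest reply is that this is loose wording and not a rule. The numbered definition agrees across both documents and would normally govern, with the censoring sentence as a paraphrase. Footnote b to Protocol Table 8-1 and SAP Table 5-1 explains an alternative anticancer regimen as chemotherapy or radiation, so the phrase may be shorthand for any treatment. That is plausible, but nothing in the text says so. The same footnote also leaves completion of frontline therapy undefined for a patient who switches to an antibody regimen.

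A reader might go further and infer that patients rescued with an antibody or antibody-drug conjugate are simply never events, and that the losses would fall mainly on ABVD because brentuximab vedotin would be the natural rescue there. The documents do not support this.

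- Under the censoring paragraph these patients are events.
- The third component is not limited to the first subsequent therapy. Later chemotherapy or radiotherapy triggers it, dated back to the first non-CR PET, so scans missed in between do not move it.
- Progression and death still count, subject to the missed-visit rule. Protocol 7.10 itself requires CT until study closure, which conflicts with its own end to mPFS visits.
- The status of an antibody-drug conjugate is open. Protocol 5.2 lists "Prior immunosuppressive chemotherapy, therapeutic radiation, or any immunotherapy (eg, immunoglobulin replacement, other monoclonal antibody therapies") as separate classes, but that is an eligibility washout. Protocol 6.4 calls the frontline treatment of both arms chemotherapy, and Protocol 1.2 describes brentuximab vedotin as delivering a cytotoxic.
- The US approval in Protocol 1.1.2 covers failure of autologous transplant, or of at least two multi-agent regimens in patients who are not transplant candidates. A patient with residual disease after ABVD alone is outside it.

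All five points stand. They narrow the affected group and remove any claim about direction. They do not remove the contradiction.

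**Conclusion.** The concern holds as an inconsistency in the definition of the primary endpoint. The affected patient is an IRF-confirmed non-complete responder who is rescued only with a treatment that is neither chemotherapy nor radiotherapy, never later receives either, and has no countable progression or death. That patient is an event under one sentence of Protocol 8.1.6.1 and can be informatively censored under another, and no planned sensitivity analysis shows the difference.

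The number of such patients is unknown and could be small. Equal shares in both arms leave the HR near 0.67. The worked imbalances give about 0.64 to 0.78, but they rest wholly on assumed inputs and count every such rescue as lost. They show that the HR can move either way; they do not predict a loss of power or a bias toward either arm. The point should be settled because the primary endpoint must have one derivation, not because a particular bias has been shown.

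**What to change.** Before any unblinded analysis, define the third component once: receipt of any subsequent anticancer therapy for HL (systemic therapy of any class, transplant or radiotherapy) after completion of frontline therapy, in patients who are IRF-confirmed non-complete responders. This settles antibodies, immunotherapies and antibody-drug conjugates together.

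Use that one term in:

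- Protocol 8.1.6.1, in both the numbered definition and the censoring paragraph;
- Protocol 7.10, so that the event trigger matches the trigger that ends mPFS visits;
- SAP 5.8.1.1, SAP 5.8.1.2 with Table 5-2, and the new-therapy rows of SAP Table 5-3.

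The Protocol Summary, Protocol 4.1 and footnote b of the frontline-therapy tables should follow. The CT requirement and the end of mPFS visits in Protocol 7.10 should be reconciled at the same time.

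The cost is a wording amendment to both documents and the matching derivation code. No new data are needed, because Protocol 7.4.13 already records all subsequent anticancer therapies. The number of events and the sample size do not change. Protocol 6.7 keeps aggregate efficacy data blinded to the sponsor's study team, so the choice can still be made without knowledge of the results.
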